### **6.3.14 Subject Adherence Assessments and Drug Dispensing**

**Drug accountability/compliance** will be assessed at every 2-month in-person visit after Baseline (even if there is a visit in between the two months). A medication diary will be provided to all parents/caregivers of subjects at each visit from baseline to the 16 month visit (visit 14). The parent/caregivers will record all doses given and the time given in the dosing diary. To assess compliance the diary will be reviewed with the study coordinator at each visit and missed doses noted.

All bottles provided at the last study visit will be returned and empty bottles will be counted and volume remaining in partially used and unused bottles determined by approximation. Bottle counts and expected/actual bottle use will be recorded in source documents. Correspondence between study drug used and logs will be determined and discrepancies reconciled with the parents/caregivers at each study visit. If 7 or more consecutive days (14 consecutive doses) or 14 or more total days (28 total doses) are missed between any two study visits, the subject may be withdrawn from the study. If any doses are missed compliance will be reinforced with the family at the visit.

**Dispensing of Study Drug** will be done every 2-month in-person visit except Follow Up (visit 15). Amount of drug dispensed will depend on the subject's dose at the time of the visit and, for the AFQ Baseline, 8, and 16 month visits (visits 3, 9, 14), any potential allowed dose titration or weaning that may be done before the next drug dispensing visit. Sufficient study drug will be dispensed to cover all dosing until the projected next study visit at which drug will be dispensed, including the maximum length of time allowed before return by the visit window.

In the case that a visit becomes delayed outside of the visit window due to weather or other unforeseen circumstances, additional study drug can be mailed to the subject to cover dosing until the subject is able to attend the study visit, so as not to interrupt dosing.

- First, clinicians will rate parent engagement and competence with the intervention during the coaching sessions. We will use a rating system adapted from that used successfully by Kasari et al. in their research on parent-implemented interventions for children with autism.
- Second, clinicians will rate parent engagement and competence with the intervention during the parental homework sessions; again, using the adaptation of the Kasari et al. coding system.
- Finally, clinicians will query the parent about mastery and ease of use of the taught strategies and the frequency of use during the past week. These queries will occur during feedback sessions.

These three quantitative measures will be analyzed separately and in combination to determine parental mastery and use of the targeted strategies and thus the effective "dose" of the language intervention actually received by the subject.

Parents will have a worksheet (Language Intervention Diary) they can use as a tool to keep a chart of their use of the intervention strategies to include the number of times and the length of time each day the intervention was used. The time chart will be formatted like a daily planner with each day divided into blocks of time in columns on the chart and the family will color in the time period when the intervention was used. One week of time will be represented on each page of the time chart. Based on times filled in by the family, the number of times the intervention is used can be tracked by the family to help them report this information systematically to the SLP during ratings of caregiver fidelity. This Language Intervention Diary will be reviewed at study visits and kept in the source documents but not entered into CRFs. The CRFs will contain only the bulleted information above. The Language Intervention Diary may serve as a guide for site staff to review intervention compliance with the family and encourage additional use when needed.

Clinician fidelity in implementing the didactic, coaching, and homework sessions will also be rated following a rubric developed previously by [name] and colleagues. It is expected that scores of 80-90% correct will be achieved. Fidelity will be assessed for up to 10% of sessions per clinician.

The parent/legal guardian administering the language intervention for a given subject must remain the same throughout the trial. If the same parent/caregiver cannot administer the assessment, the site must contact the Study Team as soon as they become aware.

### **6.3.15 Additional Evaluations**

**Auditory ERP** can be administered by a trained study staff member. ERP has been evaluated in FXS in a few pilot studies, and provides a badly needed direct index of brain function. Auditory ERP is known to be abnormal with a larger magnitude of response in FXS due to sensory oversensitivity to sound. This is thought to relate to CNS circuit dysfunction from increased dendritic spine density in sensory cortices and lack of pruning leading to hyperactivation of sensory circuits.

A model for this has been described for the *Fmr1* knockout mouse (model of FXS) in the barrel cortex neurons that respond to whisker sensation. Thus auditory ERP may be a direct window into the synaptic dysregulation in FXS, and is similarly abnormal in the FXS mouse model and humans with FXS, making it a highly attractive measure that could be used for direct translation of drug effects from mouse to man, a gap area in outcome measure development.

ERPs are inherent components of an electroencephalography (EEG) signal, and therefore must be extracted from an EEG through signal processing techniques. An EEG signal provides a coarse measure of brain activity, which makes it difficult to use it to assess highly specific neural processes or isolate individual neuro-cognitive processes. In contrast, ERPs are a class of potentials that display time relationships to a definable event such as a sensory, a cognitive, or a motor event.

One of the main advantages of using ERPs to analyze cognitive activity is that they provide a continuous measure of processing between a stimulus and a response, which makes it possible to identify and quantify the response and stages of processing that are affected by a specific experimental manipulation. This is especially useful when studying individuals with FXS because they often have hyper reactive responses to stimuli that are auditory, tactile, visual, and olfactory. Van der Molen et al. showed that the N1 and P2 components of sensory evoked potentials from sixteen males with the FXS full mutation and twenty age-matched controls were significantly enhanced in the FXS patients. By focusing on the changes in the N1, P2, and N2 (relative to the common average reference) components of subject ERP signals, between the first and last 45 stimuli presented, Schneider et al. showed that there was abnormal electrocortical habituation to auditory stimuli in patients with FXS, and this improved at N1 and P2 in individuals with FXS who were given minocycline treatment compared to a control group.

The ERP will be administered in an EEG recording session during a single clinic or research visit for each participant at visits 1, 3, 5, 7, 9, 14, and 15. Dense array electrode recording equipment will be used. Stimuli will be presented on a separate computer using Presentation software by NeuroBehavioral Systems, Inc. Event markers synchronized with stimuli will be conveyed to the EEG system over a parallel digital interface.

If the auditory ERP cannot be administered at the screening visit, sites may administer them at the -2 month visit (v2).

When the EEG recording system is set up and the head cap is properly secured on the subject, EEG recording will begin. The EEG signal can be viewed on the designated digitization computer (Figure 1). An Alpha Block Test will be performed to make sure that alpha waves are minimized and do not distort the EEG recording and to get an Alpha Reactivity Index. Two 1 min segments of eyes-open resting EEG and two 30 sec segments of eyes-closed resting EEG will be recorded with segments marked in the EEG data. Eyes closed versus eyes open data will be compared to ensure suppression of alpha with the eyes open. The EEG will then be recorded for 10 min with the passive auditory oddball paradigm using Presentation software that will serve as an auditory stimulus. Total recording time for each subject will be about 15 minutes.

The auditory stimuli that will be used by the Presentation software will consist of 480 sinusoidal tones of frequencies 1000 Hz (standard tone) and 2000 Hz (target tone) that will be emitted from the speakers of the simulation computer. These tones will be generated using Matlab software (The Mathworks, Natick MA). The order of the tones will be randomized, consisting of six 1000 Hz standard tones and then one different 2000 Hz target tone at either the 7th, 8th, 9th, or 10th position, with 1000 Hz standard tones filling in the remaining positions. The stimulus onset-to-onset time (stimulus onset asynchrony, or SOA) will be 1 second. A bandpass filter will be set at .1 Hz-100 Hz on the EEG signal during recording of all data and will be digitized at 1024 Hz. Offline, EEG data will be filtered .5-30 Hz for ERP data analyses. This is done to remove any large electrical artifacts that may be present. Moreover, this allows for an efficient way to eliminate most noise, since ERPs of interest are usually found at less than 30 Hz.

The EEG data for each patient will first be segmented according to event type, standard or target tone using a 1000 ms window with 100 ms before the event (the tone) and 900 ms after the event. The purpose of this segmentation is to generate an easy reading frame to analyze the data both before and after a tone. In order to obtain each individual's ERPs, the EEG signal must be averaged. Each participant's EEG will be averaged and baseline corrected using the signal data from the 100 ms interval before an event (before a tone). When the ERP is successfully separated from the original EEG signal for each participant, the significant auditory ERP components will be identified at each of the electrode positions. Although there are several components to an ERP, the most significant known auditory ERP components in the age range studied are P1, P2, and N2. Only the electrode sites that display the largest voltage deflections for these three components with respect to the appropriate reference for that component will be selected for statistical analysis and comparisons. Amplitudes for P1, P2 and N2 components, habituation of these components between the first 45 and last 45 stimuli presented, a mismatched negativity measure (MMN) which is the earliest ERP indicator of cortical auditory processing in a passive listening paradigm, and resting state measures with eyes open and closed will be obtained from the ERP software. All ERP data will then be uploaded to SharePoint (University of Oklahoma) for central analysis.

The ERP portion of the trial will not occur at all sites. It is expected that only a subset of subjects – approximately 50% – will complete this procedure as part of the study. This is due to concerns over site equipment as well as difficulty in terms subject cooperation in this particular population.

Administration time: 20-30 minutes with subject, depending on set up time, recording will be 15 minutes.

**Computerized Eye-Tracking** will be done with the subjects at Screening, AFQ Baseline and 2, 4, 8, 16 month and Follow Up visits (visit 1, 3, 5, 7, 9, 14, and 15). This assessment can be

AFQ056 for Language Learning in Children with FXS  
Version v15  
Version date 02/03/2021

administered by a trained study staff member. Gaze avoidance is a hallmark behavioral feature of FXS and individuals with FXS have difficulty in establishing and maintaining eye-gaze during social interactions. Studies have shown that pupillary responses are regulated by the autonomic nervous system in part in response to level of emotional arousal. A computerized eye-tracking device (Tobii) will be used employing a standardized protocol that is suitable for individuals of varying ages with FXS.

If the eye tracking cannot be administered at the screening visit, sites may administer them at the -2 month visit (v2).

Subjects will be required to look at a screen for approximately 10 minutes while 60 images of human faces with differing emotional content (happy, calm, fearful) will be presented alternating with scrambled faces. Automated assessments of time spent looking at and number of fixations on regions of interest (e.g. eyes, nose, mouth) in face images will be recorded. Changes in pupil diameter will be measured associated with viewing of faces as an index of autonomic arousal. Data from the Tobii eye tracker will be analyzed according to the method of Farzin et al. and output including time looking at and fixations to regions of interest during each type of face presentation, as well as pupil diameter changes relative to scrambled face background for each type of face presentation will be collected. All eye tracking data will then be uploaded to SharePoint (UC Davis) for central analysis.

It is expected that only a subset of subjects – approximately 50% – will complete this procedure as part of the study. This is due to concerns over difficulty in terms subject cooperation in this particular population.

Administration time: 15-30 minutes with subject.

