### 9.5.3 Other Secondary & Exploratory Outcomes

#### Safety Endpoints

The number of adverse events (AEs) and serious adverse events (SAEs) will be tracked over time. Counts will be statistically compared among the AFQ056 and placebo groups to evaluate safety in regards to whether levels are statistically equivalent over time. This will be looked at separately during the main study phase and extended study phase. In order to evaluate safety, the following will be assessed.

- Safety measures including clinically significant laboratory values and adverse events tabulated for descriptive comparison between the placebo and active drug groups.
- Tolerability, defined as the ability to at least continue treatment after the dose has been reduced to the lowest allowed dose (12.5 mg) due to side effects. The necessity to discontinue treatment after dose reduction to 12.5 mg would be considered lack of tolerability.

**Biomarker Exploratory Outcomes:** Another key secondary objective of this study is to show improvement in specific measures from ERP biomarkers in the combination of the AFQ056/language intervention group relative to those in the language intervention/placebo group. To address this objective, a number of key secondary biomarker endpoints will be obtained:

- ERP
  - Auditory habituation first 15% versus last 15% for amplitude of pediatric p50/N1 (P1) peak occurring at approximately 100 ms post-stimulus
  - Amplitude of auditory response at three components: pediatric p50/N1, N2, and P2
- Eye Tracking
  - Percent of looking time to eyes (all conditions)
  - Number of fixations to eyes (all conditions)

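### ERP electrodes are chosen by the size of the response that is then the endpoint, and the unit of selection is not stated; chosen per recording, amplitude is inflated more when fewer trials are usable

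*Combined protocol and SAP*

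**What the plan says.** Section 6.3.15 (Auditory ERP) sets out the sequence. The recording uses many sites: "Dense array electrode recording equipment will be used". Then "Each participant's EEG will be averaged and baseline corrected using the signal data from the 100 ms interval before an event". Components are next identified at every electrode position. Finally, "Only the electrode sites that display the largest voltage deflections for these three components", judged against the reference suited to each component, "will be selected for statistical analysis and comparisons". The components are P1, P2 and N2.

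Section 9.5.3, under the biomarker exploratory outcomes, lists as endpoints "Amplitude of auditory response at three components: pediatric p50/N1, N2, and P2" and "Auditory habituation first 15% versus last 15% for amplitude of pediatric p50/N1 (P1) peak". The quantity that picks the sites is therefore the quantity that is analysed.

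The plan names no site or cluster in advance. It does not say whether sites are picked per child, per visit or from pooled data, or how many are kept. Section 6.3.15 describes filtering, but gives no rule for rejecting epochs and no minimum number of accepted trials. Section 9.6.3 says only that the ERP score can be handled like the primary endpoint. The opening of Section 9 promises a formal analysis plan, but nothing in the documents completes the rule.

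**The concern.** The largest of several noisy averages overstates the true response, because selection favours sites where noise happened to add to the signal. The overstatement shrinks as more trials enter the average. Measured amplitude then depends partly on how many clean trials a child gave, with no change in cortical response.

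Two uses of the data are exposed.

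- **The drug comparison.** Section 6.3.15 describes enlarged auditory responses in FXS, and Section 9.5.3 cites an mGluR5 blocker lowering N1 amplitude in mice, so a fall in amplitude is the result of interest. Section 7 lists hyperactivity and irritability among the expected side effects. These could change clean-trial counts on drug.
- **Within-group comparisons over visits.** Section 2.1 plans to follow the ERP trajectory over the longer study period. Section 9.6.3 plans rate-of-change comparisons within the placebo-assigned group and a comparison of the follow-up visit with month 16. No randomised contrast removes the bias there. If children sit better as they grow older, clean trials rise and measured amplitude falls, which would look like normalisation.

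**Working it through.** The plan gives no ERP variance, power or detectable effect, so there is no ERP figure to reproduce.

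**Inputs from the documents.** 480 tones per recording. About 50% of 100 subjects are expected to complete ERP, randomised 1:1, so 100 × 0.5 / 2 = 25 per arm.

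**Step 1: size of the inflation.** Assumptions not in the documents: true amplitude 3 microvolts at six sites and zero elsewhere, single-trial noise SD 10 microvolts, inter-site noise correlation 0.5. Noise shared by all sites does not affect which site is largest. The site-specific noise SD after n trials is

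s(n) = 10 × √(1 − 0.5) / √n = 7.07 / √n,

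so s(430) = 0.341, s(100) = 0.707 and s(45) = 1.054. If the m largest of the six active sites are averaged, the expected amplitude is 3 + c_m × s(n), where c_m is the mean of the top m expected order statistics of six standard normals (1.267, 0.642, 0.202, −0.202, −0.642, −1.267):

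- c_1 = 1.267
- c_4 = (1.267 + 0.642 + 0.202 − 0.202) / 4 = 0.477
- c_6 = 0

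| Sites kept | 430 trials | 100 trials | Shift |
|---|---|---|---|
| Largest one | 3 + 1.267 × 0.341 = 3.43 | 3 + 1.267 × 0.707 = 3.90 | 0.46 |
| Largest four | 3 + 0.477 × 0.341 = 3.16 | 3 + 0.477 × 0.707 = 3.34 | 0.17 |
| Largest six | 3.00 | 3.00 | 0 |

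Simulation with 32, 64 or 128 sites agrees: the top-six mean reaches only 3.01 to 3.02 at 100 trials. At 45 trials the single largest site gives 3 + 1.267 × 1.054 = 4.34. The top-six row is the favourable case, since six is the assumed number of active sites. With very few trials, silent sites start to enter the top six and its bias is no longer negligible.

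**Step 2: effect on the arm comparison.** This is a separate simulation of the single-largest-site rule applied per recording. Assumptions: nine electrodes, correlation 0.5, true peak 4 microvolts with a 1 microvolt fall-off across sites, between-child SD 2, trial noise SD 10 to 20, 25 per arm, t-test at 0.05. Bias is drug minus placebo.

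| No true effect: clean trials, drug v placebo | Bias (microvolts) | Type I error |
|---|---|---|
| 45 v 45 | about 0 | 0.049 to 0.054 |
| 432 v 216 | −0.17 to −0.40 | 0.064 to 0.098 |
| 45 v 22 | −0.64 to −1.33 | 0.148 to 0.246 |

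With a true reduction of 1.5 microvolts and fewer clean trials on drug (22 v 45), the estimate shrinks to −0.85 (noise SD 10) or −0.16 (noise SD 20). With more clean trials on drug (60 v 30), it grows to −2.03 or −2.62.

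**Step 3: the alternatives.** Over the same null scenarios, four sites fixed in advance give bias within 0.02 microvolts and type I error 0.047 to 0.054. Sites chosen once from the average pooled over arms give bias of at most 0.24 microvolts and type I error 0.044 to 0.057.

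**Step 4: habituation.** If sites are picked on the whole-recording average and then used in both blocks, simulation with 64 sites and no true habituation gives bias within 0.04 microvolts. The block length is itself inconsistent. Section 6.3.15 specifies "habituation of these components between the first 45 and last 45 stimuli presented", which is 45/480 = 9.4%, while the 15% in Section 9.5.3 is 0.15 × 480 = 72 stimuli.

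**The case against.** The strongest reply is that the text speaks of sites in the plural, so a single-maximum calculation overstates the effect. That stands: the shift from 430 to 100 trials is 0.17 microvolts for four sites and about zero for six, and 0.46 should not be quoted alone.

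A reader might also infer that the rule will produce a false drug effect. The documents do not support that. It needs selection per child or per recording, which is the natural reading of the sequence but is not stated. It also needs clean-trial counts that differ by arm, and none is documented. Section 7 expects side effects to be relatively infrequent, mild to moderate, and mostly handled by dose adjustment during titration. For a modest deficit the effect is small even with a single site: 430 v 340 trials gives 1.267 × 7.07 × (1/√340 − 1/√430) = 0.05 microvolts. The larger error rates above require one arm to have half the trials of the other.

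Nor is any use of post-randomisation data a fault in itself, since selection pooled over arms is nearly harmless. Habituation, which Section 9.5.3 calls the major biomarker outcome, is largely protected if sites are picked on the whole recording.

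What remains is that the wording permits the biased version and nothing excludes it. Equal counts between arms also do not protect the within-group comparisons. A change from baseline does not remove the bias either, if trial counts change over visits differently by arm.

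**Conclusion.** The concern holds in a limited form. The plan selects ERP electrodes on the endpoint and leaves the unit of selection open. Chosen per child or per recording, measured amplitude is biased upward, and the bias grows as usable trials fall. The direction does not depend on the assumed values. The size does: it rests on assumed noise, correlation and scalp pattern, and on how many sites are kept. The bias cancels between arms when trial counts are similar; it can mimic, hide or enlarge a drug effect when they are not. The within-group comparisons over visits are exposed whenever trial counts change with age or cooperation.

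This affects a biomarker outcome under an exploratory heading in Section 9.5.3, although the same section also calls it key secondary. It does not touch the primary endpoint. It is a cheap improvement worth making before unblinding, not a flaw that undermines the trial.

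**What to change.** Replace the selection sentence in Section 6.3.15. For each component, fix one electrode cluster from the grand average of the pre-randomisation recordings (screening and visit 3, all children, arm masked). Use that cluster for every child, visit and habituation block. Report the number of accepted trials by arm and visit, state the epoch-rejection rule and minimum trial count behind that number, and reconcile the two habituation block lengths.

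The peak measure can stay. Mean amplitude in a fixed window is an option, but curing the site selection does not require it.

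The cost is analysis-plan wording. The recordings are already scheduled and analysed centrally, so no new data are needed. The small downside is that children with unusual scalp maps are measured slightly off their own peak.
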